10 STUDY PROCEDURES

10.1 VISIT SCHEDULE

The schedules of study assessments for all patients enrolled in this study are provided in [Section 1.2](#). The individual evaluations are described in [Section 9](#) and will occur before infusion with study drug, unless otherwise noted, and during approximately the same time for each visit (in reference to the screening/baseline visit). When multiple assessments are required, the order will be vital signs before ECG before blood draw.

Day 1 is the day the first infusion is administered. The study visit schedule will be calculated using the date of Day 1 of the dose escalation period as the reference.

Infusions will take place in a hospital. All infusions will take place in a monitored setting with ready access to emergency resuscitation equipment and medications.

Patients will complete the eDiary at these time points:

- Early in the screening period to verify inclusion criterion I06
- Before the first infusion to collect baseline data (see [Section 9.1.4.4](#)).
- At least 7 days before each quarterly visit of the PAP and ETP.
- At end of study (EOS)/early discontinuation

To collect patient responses to the composite endpoint, patients will enter responses in the eDiary device during the evening of the 7 consecutive days before Day 1 and each quarterly visit, separately, of the PAP and the ETP. Sites will distribute and collect the eDiary device according to the schedule presented in [Section 1.2](#). Patients will make entries into the eDiary device at home according to the schedule provided in [Section 1.3](#).

Rescreening may be possible for patients who screen failed, but is subject to sponsor approval. Imaging, function tests (eg, PFTs, ergometry), and questionnaires performed within 12 weeks of the expected date of randomization can be used for rescreening. All labs will be repeated, except genotyping and ASM activity measurements. The eDiary will not be repeated.

In-patient hospitalization will be required before the start of the infusion and until at least 24 hours after the end of infusion during dose escalation (ie, through Week 16 [PAP]/Week 70 [ETP] if no dosing adjustments are necessary) and may be required during quarterly visits up through the end of Year 2; in-patient hospitalization may be necessary during quarterly and yearly study visits in Years 3 through 5. Blood will be collected and safety assessments performed 24 and 48 hours after the end of infusion. After the cut-off date for a planned second database lock of the study for purpose of regulatory submissions in 2021, the 48 hours post-infusion blood samplings will no longer be collected. For all other visits, patients will be observed after the end of infusion for at least 1 hour. Study drug infusions will occur once every 2 weeks (± 3 days) in

reference to the date of the first infusion (Day 1) for each patient, at the site or at home during a regional or national emergency declared by a governmental agency such as the COVID-19 pandemic (refer to [Appendix B](#) for Germany) if agreed between the investigator and the sponsor for eligible patients, in compliance with applicable country-specific regulations. Quarterly visits will occur at the site. If site visits are not possible and home infusion is already approved for the eligible patient, quarterly visits will be done at home. In such a case, some of the quarterly visit assessments can be done by the site through the phone (eg, [Health-related quality of life instruments](#)). The rest of the missed quarterly visit assessments will be done as unscheduled, as soon as site visits become available.

Telehealth visits are an acceptable alternative to site visits during the COVID-19 pandemic, in accordance with institutional policy and with applicable country-specific regulations. Patients who initiated home infusion during the COVID-19 pandemic, and continue to be on home infusion, may continue receiving home infusion by trained home nurses in the ETP every 2 weeks (± 3 days) until the end of the ETP (refer to [Appendix B](#) for Germany) and, in such case, telehealth visits may continue until the end of the ETP (except quarterly visits as specified above).

For the end of study/early discontinuation visit, assessments may vary depending on when discontinuation occurs.

- Patients who discontinue during the dose escalation period of the PAP or the ETP due to intolerability of 0.1 and/or 0.3 mg/kg olipudase alfa or placebo (ie, during study Weeks 0 through 6 [preinfusion]/Weeks 54 through 60 [preinfusion]) will only have:
 - Complete physical examination
 - Vital signs
 - Samples collected for the following assessments:
 - Clinical chemistry,
 - Coagulation
 - LFTs
 - Hematology
 - Urinalysis
 - hsCRP, iron, ferritin, plasma ceramide, cardiac specific troponin I, calcitonin
 - Multiplex assay
 - Anti-olipudase alfa IgG
 - β -HCG pregnancy test (if female of childbearing potential)
 - No other assessments will be performed, unless deemed necessary for safety reasons.
- Patients who discontinue during the dose escalation period of the PAP or the ETP after the Week 6/Week 60 infusion will only have:
 - Complete physical examination
 - Vital signs

- ECG
- Samples collected for the following assessments:
 - LFTs
 - Hematology
 - Urinalysis
 - hsCRP, iron, ferritin, plasma ceramide, cardiac specific troponin I, calcitonin
 - Multiplex assay
 - Anti-olipudase alfa IgG
 - β -HCG pregnancy test (if female of childbearing potential)
 - Sphingomyelin, ceramide, and other metabolites in plasma
 - Metabolites in dried blood spot
 - Chitotriosidase, ACE, and CCL18
 - Fasting lipid profile
- No other assessments will be performed, unless deemed necessary for safety reasons.
- For the EOS visit and for patients who discontinue after the dose escalation period of the PAP or the ETP, NPB Health Assessment, NPB-HAQ, PGIS questionnaires, abdominal MRI, liver echo Doppler, HRCT, chest X-ray, pulmonary function tests, treadmill ergometry, and echocardiogram with Doppler will not be repeated if they had been done within 3 months prior; DXA and bone MRI will not be repeated if they had been done within 6 months prior. All other assessments specified in [Section 1.2.2.3](#) will be performed.

10.1.1 Home infusions

Home infusion may be given by trained home nurses during a regional or national emergency declared by a governmental agency such as the COVID-19 pandemic (refer to [Appendix B](#) for Germany) in the ETP every 2 weeks (± 3 days), in compliance with applicable country-specific regulations. Patients must meet specific eligibility requirements outlined below. In addition, the investigator and the sponsor must agree that home infusion is appropriate for each patient. Patients who initiated home infusion during the COVID-19 pandemic, and continue to be on home infusion, may continue receiving home infusion by trained home nurses in the ETP every 2 weeks (± 3 days) until the end of the ETP (refer to [Appendix B](#) for Germany).

For a patient to receive home infusions, the following criteria must be met.

- The investigator must agree in writing that home infusion is appropriate for the patient.
- The patient must be willing and able to comply with home infusion procedures.
- The patient must, in the investigator's (or designee's) opinion, have been clinically stable with no history of moderate or severe IARs for at least 6 months, that, in the opinion of the investigator, may affect the patient's ability to tolerate the infusion.

- No infusion rate increases will be allowed while a patient is receiving home infusions.
- The patient must have no ongoing (not yet recovered) SAEs that, in the opinion of the investigator, may affect the patient's ability to tolerate the infusion.
- Home infusion infrastructure, resources, and procedures must be established and available according to applicable country-specific regulations.
- In patients experiencing an IAR while being infused at home, the investigator should assess whether or not it is safe for the patient to continue to be treated via home infusion or return to the site for the subsequent visit and when the patient would be ready to resume home infusion. In case home infusion continues, the investigator will guide the home infusion staff on the measures to be followed for subsequent infusion to manage the IAR (eg, infusion interruption, premedication, change the infusion rate, etc. (See Treatment of infusion-associated reactions in [Section 8.8](#)).
- If recurrent IARs or hypersensitivity reactions occur, the investigator should assess whether or not it is safe for the patient to continue to be treated via home infusion.
- If a severe hypersensitivity reaction or an anaphylaxis reaction occurs, during an infusion given at home, treatment will be discontinued immediately, and appropriate medical treatment will be initiated. The patient will return to the study site for further management until the investigator agrees with the sponsor that it is safe for the patient to continue to be treated via home infusion. See [Section 8.8](#) for details on severe hypersensitivity and anaphylaxis management.
- Prior to beginning home infusions, the home infusion staff, including new staff members, must have been appropriately trained and/or licensed, if applicable, on proper procedures to prepare and administer infusions, monitor patients, document procedures, and report to site on a timely basis.
- The home infusion staff must have access to and be trained on proper use of safety equipment, including, but not limited to, cardiopulmonary resuscitation equipment.
- Home infusion staff must keep source documentation of the infusion, including documentation of any AEs, IARs, examinations/ assessments, sample collections and concomitant medication. Home infusion staff must be amenable to providing specific source documentation to Sanofi Genzyme and agree to be monitored. The Principal Investigator is still responsible for all study procedures and patient's safety even when delegating infusion responsibilities to the home care company.
- An additional questionnaire about home infusion experience may be added any time before end of the study for patients who received home infusion treatment.
- If the site visit is not possible during a regional or national emergency declared by a governmental agency such as the COVID-19 pandemic (refer to [Appendix B](#) for Germany) due to site closure or extenuating circumstances that prevent an in-person site visit, and home infusion already approved for the eligible patient, the investigator can decide whether reintroduction should occur at the hospital/study site or home visit.
- For the switch from Process C (■) IMP to the updated manufacturing Process C(■) IMP, if the site visit is not possible during a regional or national emergency declared by a

governmental agency such as the COVID-19 pandemic (refer to [Appendix B](#) for Germany) due to site closure or extenuating circumstances that prevent an in-person site visit, the first infusion of process C() IMP is allowed during home infusion for eligible patients in agreement between the Sponsor and the Investigator in compliance with applicable country-specific regulations.

10.2 DEFINITION OF SOURCE DATA

Source data are all information, original records of clinical findings, observations, or other activities in a clinical trial necessary for the reconstruction and evaluation of the study. Source data are contained in source documents. Examples of these original documents and data records include hospital records, clinical and office charts, laboratory notes, memoranda, patients' diaries or evaluation checklists, pharmacy dispensing records, recorded data from automated instruments, copies or transcriptions certified after verification as being accurate and complete, microfiches, photographic negatives, microfilm or magnetic media, X-rays, patient files, and records kept at the pharmacy, the laboratories, and other departments involved in the clinical study.

All protocol-required information collected during the study must be recorded by the investigator or other study personnel in the source documentation for the study. The source documentation will be used to enter the protocol-required information into the eCRF. No data should therefore be directly entered into the eCRF.

10.3 HANDLING OF PATIENT TEMPORARY OR PERMANENT TREATMENT DISCONTINUATION AND OF PATIENT STUDY DISCONTINUATION

Study drug will be continued whenever possible; however, if study drug is stopped, it will be determined if the stop can be made temporarily as permanent discontinuation will be a last resort. Any discontinuation will be fully documented in the source and eCRF. In any case, the patient should remain in the study as long as possible.

Pregnancy

Pregnancy will lead to treatment discontinuation in all cases. No studies of olipudase alfa have been conducted in pregnant women. To ensure patient safety for this study, all female patients of childbearing potential must have a negative serum β -HCG pregnancy test at screening and before undergoing any further assessments and procedures. Urine β -HCG will be tested up to 24 hours before the first infusion of the study; then once every 4 weeks before infusion. In addition, these patients are required to have a negative serum or urine β -HCG pregnancy test during the PAP and ETP every 4 weeks after randomization before undergoing visit specific assessments and being infused with study drug. Patients must be willing to practice true abstinence or use 2 acceptable, effective methods of contraception while they are participating in the study. If a patient is no longer participating in the study, they must practice true abstinence or use 2 acceptable, effective methods of contraception for 15 days following their last dose of study drug. Every effort will be made to prevent pregnancy during this study.

In all cases, the sponsor must be notified of all terminations to treatment as soon as possible and, if applicable, the date of withdrawal from the study must be recorded in the eCRF and in the patient's medical record. If possible, all tests and evaluations listed for the end of study visit will be carried out. If a patient fails to return for the necessary visits, then every effort must be made to contact the patient and determine the reason(s), which will be recorded on the eCRF.

Alcohol consumption

Although blood alcohol testing will not be required, patients must be willing to abstain from the use of alcohol for 1 day before and 3 days after each study drug infusion ([Section 7.2](#)).

Patients will be counseled to limit alcohol consumption during the study:

- Male patients to a maximum of 30 g alcohol per day (2 drinks/day)
- Female patients to a maximum of 15 g alcohol per day (1 drink/day)

Patients who do not limit alcohol can be discontinued from the study, according to investigator's discretion.

10.3.1 Temporary treatment discontinuation with investigational medicinal product(s)

Temporary treatment discontinuation corresponds to more than 1 dose not administered to the patient as decided by the investigator after consultation with the sponsor.

Temporary treatment discontinuation (also referred to as treatment interruption) may be considered by the investigator because of suspected AEs.

Re-initiation of study drug administration will be done under close and appropriate clinical/and or laboratory monitoring after the investigator has considered to his/her best medical judgment that the responsibility of study drug in the occurrence of the concerned event was unlikely and if the study selection criteria are still met ([Section 7.1](#) and [Section 7.2](#)). Before re-initiation of treatment, the sponsor must be consulted to determine the starting dose and if dose escalation will be required (see [Section 8.1.3](#)).

For all patients who have missed two or more doses that require reintroduction of olipudase alfa, the dose reintroduction will take place at the site. During the COVID-19 pandemic, if site visits are not possible and home infusion is already approved for the eligible patient, the investigator can decide whether reintroduction should occur at the hospital/study site or home visit.

Upon reintroduction of treatment, certain assessments will be repeated at infusions ([Section 8.1.3.2](#)). The investigator will decide if additional specific assessments may be required before the patient can begin the reintroduction regimen.

For all temporary treatment discontinuations, the duration will be recorded by the investigator in the appropriate screens of the eCRF.

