7 SELECTION OF PATIENTS

7.1 INCLUSION CRITERIA

- I 01. The patient is willing and able to provide signed written informed consent.
- I 02. The patient is male or female, aged 18 years or older.
- I 03. The patient has documented deficiency of ASM as measured in peripheral leukocytes, cultured fibroblasts, or lymphocytes; and a clinical diagnosis consistent with NPD B.
- I 04. The patient has $DL_{CO} \leq 70\%$ of the predicted normal value.
- I 05. The patient has spleen volume ≥ 6 multiples of normal (MN) measured by MRI; patients who have had partial splenectomy will be allowed if the procedure was performed ≥ 1 year before screening/baseline and the residual spleen volume is ≥ 6 MN.
- I 06. The patient has an SRS ≥ 5 .
- I 07. Female patients of childbearing potential must have a negative serum pregnancy test for beta-human chorionic gonadotropin (β -HCG).
- I 08. Female patients of childbearing potential and male patients must be willing to practice true abstinence in line with their preferred and usual lifestyle, or use 2 acceptable, effective methods of contraception for up to 15 days following their last dose of study drug.

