7.2 EXCLUSION CRITERIA

Patients who have met all the above inclusion criteria listed in [Section 7.1](#) will be screened for the following exclusion criteria:

- E 01. The patient has received an investigational drug within 30 days before study enrollment.
- E 02. The patient has a medical condition, including significant intercurrent illness; significant cardiac disease (eg, clinically significant arrhythmia, moderate or severe pulmonary hypertension or clinically significant valve dysfunction, or $<40\%$ left ventricular ejection fraction by echocardiogram ECHO); active hepatitis B or hepatitis C, or infection with human immunodeficiency virus (HIV); malignancy diagnosed within the past 5 years (other than non-melanoma skin cancer), or any other serious medical condition that may preclude participation in the study.
- E 03. The patient has a platelet count $<60 \times 10^3/\mu\text{L}$ based on the average of 2 samples.
- E 04. The patient has an international normalized ratio (INR) >1.5 .

- E 05. The patient has alanine aminotransferase (ALT) or aspartate aminotransferase (AST) >250 IU/L or total bilirubin >1.5 mg/dL (except for patients with Gilbert's syndrome).
- E 06. The patient has had a major organ transplant (eg, bone marrow or liver).
- E 07. The patient is scheduled during the study for in-patient hospitalization including elective surgery and excluding the liver biopsies required per protocol.
- E 08. The patient, in the opinion of the investigator, is unable to adhere to the requirements of the study.
- E 09. The patient is unwilling or unable to abstain from the use of alcohol for 1 day before and 3 days after each study drug infusion. Testing for blood alcohol levels will not be required.
- E 10. The patient is unwilling or unable to avoid 10 days before and 3 days after the protocol scheduled liver biopsies, that are required at screening/baseline, at Week 52 and at Week 104, the use of medications or herbal supplements that are potentially hepatotoxic (eg, 3-hydroxy-3-methyl glutaryl coenzyme A reductase inhibitors, erythromycin, valproic acid, anti-depressants, kava, echinacea) and/or may cause or prolong bleeding (eg, anti-coagulants, ibuprofen, aspirin, garlic supplements, ginkgo, ginseng).
- E 11. The patient requires medications that may decrease olipudase alfa activity (eg, fluoxetine, chlorpromazine, tricyclic antidepressants [eg, imipramine, or desipramine]).
- E 12. The patient requires use of invasive ventilatory support.

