8.1.4 Dose-limiting toxicities

For the purpose of this study, the events listed below are considered indicative of a potential DLT for study drug at a given dose. If a potential DLT is observed, dosing will be temporarily stopped in an individual patient or in the entire study, and the DMC will review the safety data. The DMC will then provide recommendation(s) to the sponsor regarding further patient treatment ([Section 6.4](#)). Screening for eligible patients may continue during DMC review of patient or study stopping events.

If any of the following AEs occur, dosing will be temporarily stopped for the specific patient who experienced the AE, pending DMC review and recommendation (taking into consideration the relatedness of the AE to study treatment):

- Any SAE, not related to the patient's underlying condition and considered related to the study treatment.
- Any increase in AST, ALT, total bilirubin, or alkaline phosphatase (AP) >3x baseline (prior to olipudase alfa therapy) and > the upper limit of normal (ULN).
- Any increase in total bilirubin or AP >1.5x baseline in the presence of AST or ALT >2x ULN.
- Any increase in ALT or AST >3x the ULN combined with an increase in ALT or AST >2x baseline (prior to olipudase alfa therapy) with symptoms of fatigue, nausea, vomiting, right upper quadrant pain or tenderness, fever, rash, or eosinophilia (> ULN).
- Any AE that, in the opinion of the investigator or sponsor, raises significant concern regarding the safety of olipudase alfa at the administered dose.

When study drug dosing is interrupted for a particular patient, safety monitoring of the patient will continue. If the AE(s) is/are reversible and the clinical laboratory tests (including LFTs) have normalized, the patient will resume dosing and receive the previously-tolerated lower dose (ie, dose administered on a previous week without incident). Depending on the patient's response, dose escalation will either continue (as described in [Section 8.1.1](#)) or the patient will remain at the previously tolerated dose (ie, the patient's HTD).

The investigator is responsible for notifying the Institutional Review Board/Independent Ethics Committee (IRB/IEC) in writing when a potential DLT is being evaluated at an investigative site.

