8.1.6 Rescue treatment

If during the course of the study, a patient satisfies one or more of the following criteria indicative of clinical decline due to ASMD progression and after excluding other possible causes, study drug will be unblinded and the patient will be switched to the 3.0 mg/kg olipudase alfa group; dose escalating procedures and caveats provided in [Table 1](#) and [Section 8.1.3](#) will apply. See the study manual and the IXRS manual for unblinding procedures.

- Hemoglobin level falls below 7 g/dL and remains below 7 g/dL when hematology laboratory testing is repeated after approximately 2 weeks.
- Platelet count falls below 30 000/mm³ and remains below 30 000/mm³ when hematology laboratory testing is repeated after approximately 2 weeks.
- A clinically significant bleeding episode assessed by the investigator as related to a low platelet count.

These patients will continue to be followed in the study. Upon confirmation of the need for rescue treatment, patients will have organ volume MRI and PFTs performed if prior tests were performed more than 12 weeks before.

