Because skeletal involvement can lead to osteopenia or osteoporosis, common manifestations of ASMD and splenomegaly have been shown to be inversely correlated with lumbar spine bone mineral density Z-scores (30), the severity of bone disease will be measured at baseline and once every year. A biomarker for bone resorption, C-telopeptide concentrations in serum have been shown to be decreased in patients with Gaucher disease.

Although hemoglobin level, platelet count, and white blood cell count will comprise part of the standard safety laboratory assessments, these parameters are often abnormal in patients with ASMD because many cells of the reticuloendothelial system originate in the bone marrow and it is one of the most extensively involved organs in ASMD (31, 32). Bone marrow involvement, combined with hypersplenism, contributes to the thrombocytopenia, anemia, and to the neutropenia sometimes observed in patients with ASMD.

Biomarkers will be measured that are known to be associated with macrophage proliferation (ACE), secreted by activated (NP cells) macrophages (chitotriosidase and CCL18), and

inflammatory background triggered in sphingolipidoses (bone-specific alkaline phosphatase, C-telopeptide). Changes in these biomarkers have supported the clinical responses observed with enzyme-replacement and substrate-reduction therapies in other sphingolipidoses such as Gaucher disease Type 1 and Fabry disease (33, 34, 35). The initial objective to monitor ACE changes through 52 weeks of treatment for all patients has been achieved; no further longitudinal analysis is required after the cutoff date for a planned second database lock of the study for purpose of regulatory submissions in 2021. CCL18 and chitotriosidase will continue to be monitored to assess overall disease burden.

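### Section 10.3.1 ties restart after an adverse-event hold to all entry criteria, so a patient who has improved past I04, I05 or I06 could not restart as the rule is written

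*Protocol*

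**What the plan says.** **Restart rule.** Section 10.3.1 defines a temporary discontinuation as more than one dose not given, by decision of the investigator after consulting the sponsor. Such an interruption "may be considered by the investigator because of suspected AEs". Re-initiation needs two things: the investigator must consider "that the responsibility of study drug in the occurrence of the concerned event was unlikely and if the study selection criteria are still met", with a cross-reference to Sections 7.1 and 7.2. The sentence that follows says "the sponsor must be consulted to determine the starting dose and if dose escalation will be required"; it says nothing about waiving a criterion.

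**What the cross-reference brings in.** Section 7.1 contains three disease-severity criteria: I04 (DLco no higher than 70% predicted), I05 (spleen of at least "6 multiples of normal (MN) measured by MRI") and I06 (SRS of at least 5). Section 7.2 adds the exclusions, among them E03, which begins "The patient has a platelet count" and sets the limit at below 60 x 10^3/µL.

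**Neighbouring rules.** Section 10.3 wants drug continued where possible, with permanent discontinuation only as a last resort. Section 8.1.4 stops dosing for a potential DLT, "pending DMC review and recommendation (taking into consideration the relatedness of the AE to study treatment". It then has the patient resume at a lower tolerated dose if the event is reversible and laboratory values have normalized. Section 8.1.3.2 sets the reintroduction dose from the last dose and the number of doses missed. It also lets treatment be withheld for transaminase rises during escalation. Neither section sets a causality or eligibility condition for restart.

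**The concern.** I04, I05 and I06 select patients who are ill enough to enrol. Spleen volume, DLco and SRS are also the measures the drug is meant to improve. Once these entry criteria become restart criteria, success on any one of them is a reason to refuse further drug. The patients most exposed are those treated for some time, who then have an adverse event judged unlikely to be drug-related and miss two or more infusions.

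The rule is also hard to apply. The reintroduction assessments in 8.1.3.2 cover general appearance, vital signs, liver function, hematology, safety biomarkers and pregnancy testing. They include no MRI, pulmonary function test or eDiary. A site would have to use the last scheduled values, order extra tests, or set the rule aside and depart from the protocol.

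The secondary issue is the causality condition. Read literally, it blocks restart after any drug-related hold of more than one dose, while 8.1.4 and 8.1.3.2 allow dosing to continue after such events.

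**Working it through.** The plan gives no figure for this rule, so there is none to reproduce. The check is a comparison of texts plus an illustration.

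**1. Is anything exempted?** Section 10.3.1 cites 7.1 and 7.2 without qualification. Neither the protocol nor the SAP limits the recheck to some criteria. The investigator's discretion in 10.3.1 covers causality, the site of reintroduction and additional assessments. The sponsor's role covers starting dose and escalation. So the plain reading is that all criteria apply.

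**2. Can an average responder cross a limit?** Inputs are the limits in 7.1 and the planned Week 52 differences in Protocol 11.2 (spleen 30%, DLco 25%, SRS 8.0 points). Assumption: the planned difference from placebo equals the within-patient change, that is, zero placebo change. Half the planned effect is shown as a second assumption.

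| Criterion | Planned effect | Half the planned effect |
|---|---|---|
| I05, spleen falls below 6 MN | 6/(1 − 0.30) = 8.57: baseline below 8.6 MN | 6/(1 − 0.15) = 7.06: baseline below 7.1 MN |
| I04, DLco rises above 70% | 70/1.25 = 56.0: baseline above 56% | 70/1.125 = 62.2: baseline above 62% |
| I06, SRS falls below 5 | 5 + 8 = 13: baseline below 13 | 5 + 4 = 9: baseline below 9 |

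With the 25.3% mean spleen reduction at 26 weeks in the Phase 1b study (Protocol 4), the spleen figure is 6/(1 − 0.253) = 8.03 MN. Crossing any one limit is enough.

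**3. Spread around the mean.** Adding the planned SDs (11.8% and 20%) and normality, the chance of crossing from baseline b is Φ((100(6/b − 1) + 30)/11.8) for spleen and 1 − Φ((100(70/b − 1) − 25)/20) for DLco.

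- Spleen: 0.66 at 8 MN, 0.20 at 10 MN, 0.05 at 12 MN and 0.006 at 15 MN.
- DLco: 0.66 at 60%, 0.23 at 50% and 0.006 at 40%.

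At the SAP's cut-offs for severe disease (above 15 MN, below 40%), the chance is therefore negligible on these two criteria.

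**4. The causality condition, side by side.**

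- DLT: one of the 8.1.4 triggers is an SAE considered related to treatment. After DMC review, resumption depends on reversibility and laboratory values. Under 10.3.1 the same event would fail the causality condition if 10.3.1 applied.
- Transaminases: the 8.1.3.2 hold can start above 2x baseline and above ULN, while the general DLT limit is above 3x baseline and above ULN. A rise between 2x and 3x that meets no other DLT criterion is a hold without a DLT. The rationale for amended protocol 13 (Appendix C) lists these rises as an identified risk of the drug. The rule applies only during escalation or re-escalation, and 10.3.1 is reached only if more than one dose is withheld.

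**5. Time left.** Appendix C places the first data cutoff, at the end of the PAP, on 17 October 2019. If the last patient had finished the PAP by then, four years of extension (6.2.1) end about 17 October 2023. From 01 November 2022, the date of amended protocol 15, that is 350 days, or 350/14 = 25 infusions at most.

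**The case against.** **The recheck was surely meant as a safety check.** The reintroduction assessments fit that intent, and no refused restart is recorded. This probably describes what sites do. It does not change what the text requires, and a site that ignores I04 to I06 departs from the protocol.

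**DLT holds are outside 10.3.1.** A reader might infer that 10.3.1 and 8.1.4 flatly contradict each other. The documents do not support that. Section 10.3.1 concerns interruptions decided by the investigator, whereas a DLT hold is imposed by the protocol and has its own resumption rule. Section 8.7.1 likewise treats doses missed because of a DLT as required by the protocol, and 10.3.3 makes unacceptable toxicity, with reference to 8.1.4, a ground for permanent discontinuation. This objection stands: the sections can be reconciled, but no text says which governs.

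**The transaminase case is narrow.** This also stands. On the timeline above, initial escalation in the extension (Weeks 54 to 70) had ended well before November 2022, so only re-escalation after an earlier interruption remains.

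**A platelet check at restart is sensible.** A reader might infer that E03 should be waived as well. Section 9.7 says marrow involvement with hypersplenism "contributes to the thrombocytopenia, anemia, and to the neutropenia sometimes observed in patients with ASMD", and under the rescue rule in 8.1.6 for persistently low platelets "study drug will be unblinded and the patient will be switched to the 3.0 mg/kg olipudase alfa group". The comparison fails. Section 11.4 confines rescue to the PAP, and rescue addresses ASMD progression after other causes are excluded. Restart follows a suspected adverse event, which could itself be a bleed or a platelet fall. E03 should stay available.

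**The break-even baselines are not patient data.** This is correct. They treat between-arm Week 52 planning differences as within-patient change and are illustrative only.

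**Conclusion.** The point holds for I04, I05 and I06. As written, 10.3.1 can refuse restart to a patient because disease measures improved, against the stated aim of 10.3. The causality condition is a secondary ambiguity about which section governs restart after a drug-related hold.

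The effect is limited. It needs an adverse-event hold of more than one dose in a patient who has crossed a limit. The documents give neither a baseline distribution nor an interruption rate, so the number of such patients cannot be estimated. The time left is bounded by the cutoff and four-year assumptions above.

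A reader might infer that the rule distorted the Week 52 comparison by taking responders off drug. Nothing supports this: the PAP is closed, no refused restart is documented, and Protocol 11.5.2.1 plans to use observations whatever the treatment discontinuation status. SAP Section 3 describes efficacy analysis in the extension as exploratory. What remains is treatment continuity for individual patients in the extension. Confidence is medium, because the defect is plain in the text but its operation is not shown.

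**What to change.** Amend 10.3.1 to state that:

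- (a) I04, I05 and I06 apply at entry only and are not rechecked at re-initiation;
- (b) the recheck covers I07 (pregnancy test), I08 (contraception) and those exclusions in 7.2, including E03, that the investigator and the sponsor judge relevant to safe re-dosing given the event that caused the hold;
- (c) resumption after a DLT follows 8.1.4, including the DMC recommendation, and resumption after a transaminase hold that is not a DLT follows 8.1.3.2, in both cases without requiring that drug responsibility be judged unlikely.

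The cost is about three sentences, with the ethics approval that Section 15 requires for any amendment. No visits, tests or analyses are added. The documents mention no further planned amendment, so with so little extension time left this is a low-priority correction, best carried with any other change.
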